## **10. Analysis**

### **10.1. Outcome measure**

The primary measure of physical activity will be a continuous variable that represents the average total physical activity level of each child, expressed as a mean counts per 15 seconds (cp15s) averaged over all of the child's eligible wear time on all days that meet criteria for inclusion.

Due to the young age of the participants, compliance for a full 7 days may prove to be difficult; therefore we will use 3 days of data as the minimum number of valid days per child. If a child has more than 7 days of eligible wear time, we will include all additional days with sufficient wear time.

Accelerometry data is collected at 30 Hz, meaning that data measures are collected 30 times per second. Activity counts collected within the 30 measures/second are averaged to provide an activity count for that particular second. We will be analyzing the data in sections of 15 seconds, therefore we will be averaging activity counts within 15 second intervals (average 15 data points of activity counts). These 15 second epochs (cp15s intervals that have been analyzed) will be used to analyze physical activity levels by categorizing them into sedentary behaviour (SED; sitting, laying down, etc.), light physical activity (LPA; walking, crawling, etc.), and moderate-to-vigorous physical activity (MVPA; running, jumping, etc.) using the cut-points chosen.

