We will use the cut-points established by Trost and colleagues:  $\leq 48$  cp15s for sedentary behaviour (SED), 49-418 cp15s for light physical activity (LPA), and  $>418$  cp15s for moderate-to-vigorous physical activity (MVPA) . These cut-points were chosen because they were derived from direct observation of a sample of toddler and preschool-aged children while wearing the ActiGraph GT1M accelerometer . Videos of the children playing were coded using a modified version of the Children's Activity Rating Scale before receiver operating characteristic curve analyses were conducted to determine the corresponding cut-points to the 3 categories of interest: SED, LPA, and MVPA . These results were found to exhibit excellent classification accuracy . They were then cross-validated against pre-existing cut-points that are established for toddlers and preschoolers, which were not found to be significantly different than the pre-established cut points established by Pate and colleagues  and those established by National Health and Nutrition Examination Survey .

We will then be able to calculate total time (minutes) as well as proportion of time (%) spent in each activity category (SED, LPA, MVPA). The overall mean cp15s for each child will be based on all 15-second epochs that occurred during eligible wear periods from the time that the caregiver indicated the child woke up until the time that the caregiver indicated the child went to sleep at. If this data is missing, we will use eligible wear periods between 8am to 8pm. This mean will exclude non-wear periods as defined above and when the accelerometer was not being worn by the child (based on daily logs collected from the caregivers via afternoon telephone call; Section 9.3.7.).

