For each child, we will calculate the mean number of minutes per day and the proportions of the child's total eligible wear time that are classified as SED, LPA and MVPA. We will also determine the proportion of days on which each child reached or exceeded 180 minutes of activity classified as LPA or MVPA, and the proportion of days on which each child reached or exceeded 60 minutes of activity classified as MVPA. These cut-offs are based on the Canadian preschooler physical activity guidelines established by Tremblay and colleagues , as there are no Bangladeshi standards available at present. If Bangladeshi guidelines are released before data analysis and reporting is completed, we will also apply those standards in our analyses.

For each child, we will establish the following parameters related to accelerometry:

- Total duration (minutes) of the potential data collection period on all days on which the accelerometer was instructed to be worn;
- Total eligible wear time (minutes), including data collected while the child was awake (from the time that their caregiver indicated that they woke up until the time that they went to sleep). If this data is not provided, total eligible wear time will be measured between 8am and 8pm. Non-wear periods will be excluded based on the following

criteria:  $\geq 20$  minutes of 0 cp15s allowing for up to 2 minutes of 0-100 cp15s in that period. A given day will be considered eligible for inclusion if there are at least 10 hours/day (600 min) between the indicated time period that the child was awake at, or between 8am to 8pm of wear time for those with missing data, after excluding non-wear periods;

- Total indoor eligible wear time (minutes; excluding non-wear periods as previously defined), based on maternal report;
- Total eligible wear time in or around the home (minutes; excluding non-wear periods as previously defined), based on combination of maternal report and GPS logging. "Around the home" will be defined as occurring in the same building or property of the home (e.g., rooftop, neighbouring apartment in the same building, common areas of the apartment building, private courtyard areas that are on the same property as the home in which the child resides).

For purposes of secondary and sensitivity analyses, we will also estimate for each child:

- Mean cp15s for indoor activity
- Mean cp15s for activity in or around the home

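### Section 10.1 removes caregiver-logged belt removals from the mean cp15s but not from total eligible wear time, so short or interrupted removals stay in the 600-minute rule and the SED/LPA/MVPA results as wear

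*Combined protocol and SAP*

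**What the plan says.** All the rules are in section 10.1 (Outcome measure) of the combined protocol and SAP.

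- **Primary measure.** Each child's mean cp15s is "averaged over all of the child's eligible wear time on all days that meet criteria for inclusion". The term for wear time is not defined at that point.
- **Rule for the mean.** After the cut-points, the plan adds: "This mean will exclude non-wear periods as defined above and when the accelerometer was not being worn by the child". The second source is "based on daily logs collected from the caregivers via afternoon telephone call". Logged removal is thus a separate exclusion, added to the algorithmic one.
- **Rule for total eligible wear time.** In the list of accelerometry parameters, the plan says "Non-wear periods will be excluded based on the following" criterion: a run of at least 20 "minutes of 0 cp15s allowing for up to 2 minutes of 0-100 cp15s in that period". The caregiver's report is used here for wake and sleep times, but logged removals are not mentioned. The indoor and home wear-time items refer back to the same definition.
- **Valid day.** "A given day will be considered eligible for inclusion if there are at least 10 hours/day (600 min") remain in the waking window, or in the default 8am-8pm window, after non-wear is taken out.
- **Activity categories.** The plan reports mean minutes per day and "proportions of the child's total eligible wear time that are classified as SED, LPA and MVPA".

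Section 9.3.5 expects the belt to come off for bathing and swimming. Section 9.3.6, item (b), records whether and when it came off during waking hours. No section extends the log exclusion to total eligible wear time.

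**The concern.** The investigators will hold a record of when the belt was off the child, and they apply it to one summary and not to the others. A motionless belt records 0 cp15s, which falls in the sedentary category (48 cp15s or less). If the zero run is too short to be flagged, that time enters the child's wear time as sedentary behaviour.

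Three things are at stake:

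- Sedentary minutes and share, a main descriptive result under Objective 1, are biased upwards, and the LPA and MVPA shares are diluted. A larger sample does not reduce this.
- Days with fewer than 600 truly worn minutes can pass as valid and count towards the three-day minimum per child. Those days also feed the mean cp15s and the day-level models of Objectives 2 and 3.
- For the same child, the mean cp15s and the category results rest on different wear time.

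**Working it through.** **1. The plan's own figure.** The only precision figure is in section 9.6: n = 60, SD 9.7, margin ±2.45 cp15s. At 95% confidence, 1.96 × 9.7 / √60 = 2.454, so it reproduces. It is not in dispute here.

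**2. Which removals escape the zero-run rule.** Twenty minutes is 80 epochs of 15 seconds, and the 2-minute tolerance is 8 epochs. Applying the rule to artificial traces gives:

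| Removal | Minutes flagged as non-wear |
|---|---|
| Still, 5, 10, 15 or 19 min | 0 |
| Still, 20, 30 or 60 min | all |
| 25, 30 or 38 min, with 1 min of handling above 100 cp15s midway | 0 |
| 45 min, with 1 min of handling above 100 cp15s midway | 44 |

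The gap is therefore confined to removals under 20 minutes and to longer ones that handling breaks into runs under 20 minutes. In these, every still epoch scores SED. Handled epochs of 49-418 cp15s would score LPA, and those above 418 MVPA.

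**3. Size for sedentary time.** The documents give no removal durations and no expected sedentary share. Assumptions: r = 10, 15 or 19 unflagged still minutes per day, T = 660 or 720 minutes truly worn, true sedentary share 50%. (T = 720 with a removal on top needs a waking window longer than the 12-hour default.)

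Apparent share = (0.5T + r) / (T + r).

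| T | r = 10 | r = 15 | r = 19 |
|---|---|---|---|
| 660 | 340/670 = 50.7% | 345/675 = 51.1% | 349/679 = 51.4% |
| 720 | 370/730 = 50.7% | 375/735 = 51.0% | 379/739 = 51.3% |

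Sedentary minutes rise by r, that is 10-19 per day. LPA and MVPA minutes do not change for still removals.

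**4. Size for day validity.** A day passes if truly worn time plus r reaches 600, so days truly worn between 600 − r and 600 minutes change status. Assume worn time is normal with SD 60 and mean μ:

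Fraction changed = Φ((600 − μ)/60) − Φ((600 − r − μ)/60).

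| μ | r = 10 | r = 15 | r = 19 |
|---|---|---|---|
| 660 | 15.87 − 12.17 = 3.7% | 15.87 − 10.56 = 5.3% | 15.87 − 9.40 = 6.5% |
| 690 | 6.68 − 4.78 = 1.9% | 6.68 − 4.01 = 2.7% | 6.68 − 3.46 = 3.2% |
| 720 | 2.28 − 1.51 = 0.8% | 2.28 − 1.22 = 1.1% | 2.28 − 1.03 = 1.2% |

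That is about 1-6% of days. With r = 15, for example, a day with 585 truly worn minutes passes.

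**5. Primary mean.** Under the rule stated specifically for the mean, logged removals are already out, and the effect comes through which days are admitted. If instead the mean were taken over total eligible wear time as defined in the parameter list, it would change by −r / (T + r): from −10/730 = −1.4% to −19/679 = −2.8%.

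**The case against.** **Most of the problem may already be handled.** Any still removal of 20 minutes or more is excluded under both rules. This stands, and it limits the point to short or interrupted removals. A reader might infer that logged removals in general are counted as sedentary wear. The documents do not support that: long still removals are caught, and handled epochs can score as LPA or MVPA.

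**The primary outcome is not really ambiguous.** A reader might infer that it has two competing definitions, because the opening of section 10.1 ties it to eligible wear time. But the later sentence is written specifically for each child's overall mean and excludes logged removals explicitly, so the natural reading is that it governs. For the same reason the 1.4-2.8% shift should not be set against the ±2.45 margin: that needs the less natural reading, plus a mean cp15s that the documents do not give.

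**Guideline results are largely untouched.** For still removals on a day that is valid either way, the 180-minute and 60-minute criteria do not change, because LPA and MVPA minutes do not. This stands.

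**The log is imperfect.** It is a telephone recall, sometimes taken the next morning, and errors of a few minutes matter most for removals under 20 minutes. An objective rule for day validity, with the log reserved for the mean, would be defensible. The plan does not present the difference as such a choice, however, and it already trusts the log for the mean.

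**A careful analyst would reconcile the two.** The text does not help. The rule for the mean refers to a definition above it that appears only below, and cites section 9.3.7 for the calls, which are in 9.3.6.

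**Conclusion.** The point holds in limited form. As written, total eligible wear time ignores the logged removals that the mean cp15s excludes. This is a stated rule that gives a biased result, not a missing detail. The bias runs towards more sedentary time when the belt lies still, and the size is modest: 10-19 minutes per day, or 0.7-1.4 percentage points on a 50% share, with about 1-6% of days changing validity. These figures rest on the assumed removal length, worn time, sedentary share and worn-time SD, and on a removal of that length every day; fewer or shorter removals give less. The primary mean is affected mainly through day selection, and directly only if its wear time is read with the definition in the parameter list. The change is worth making because it is cheap, not because the bias is shown to be large.

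**What to change.** In section 10.1, define non-wear once, before its first use, as zero-run non-wear or a caregiver-logged removal during waking hours. Apply it to the mean cp15s, total eligible wear time (including its indoor and home versions), the 600-minute rule, and all SED/LPA/MVPA minutes and proportions. Report results with algorithm-only wear time as a sensitivity analysis, which shows how far they depend on recalled times. Correct the reference for the telephone log to section 9.3.6.

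The cost is a short text change and a merge of log times already collected and already needed for the mean. Recall error in those times will enter day eligibility, and a few borderline days will fall below 600 minutes.

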## **10.2. Exposure variables**

- 1) Total area of available floor space inside the home (m^2)
- 2) Frequency that child plays outdoors
- 3) Total number of physical hazards in the home (presence of open stairwells, stove height)
- 4) Total number of fine-motor activity items available to the child
- 5) Presence of gross-motor activity items available to the child across each category (e.g., fixed, portable: ball equipment, push/pull equipment, riding equipment, rocking and twisting equipment)
- 6) Hemoglobin concentration (g/L).

Descriptions and derivations of each of these variables can be found in Table 1 (Appendix).

### **10.3. Other covariates**

Other covariates will include: preschooler sex, preschooler anthropometric measures (e.g., height-for-age z-score, BMI-for-age z-score, waist circumference, and body fat percentage), maternal anthropometric measures (e.g., BMI, waist circumference, and body fat percentage), maternal and paternal socio-economic factors (educational level and household assets), and household food security status. Descriptions and derivations of each of these variables can be found in Table 2 (continuous variables) and Table 3 (categorical variables) (Appendix).

### **10.4. Statistical Analysis**

#### **10.4.1. Primary Analysis**

Statistical analyses will be performed using STATA (College Station, TX). Data from Forms 1, 2, 3, 4, and the Accelerometry and GPS Log will be double entered in real time independently by research personnel. Data forms will be de-identified, such that only a participant ID number will be used to identify participants. Any discrepancies between data enterers will be flagged and reconciled by the student investigator. Data reconciliation will be conducted by the student investigator and will consist of reviewing the original hardcopy of the document and/or discussing the measure with the research assistant who had originally recorded it. Data review will consist of creating histograms, boxplots, and normal quantile-quantile (Q-Q) plots of each continuous variable to identify outliers and potentially implausible data.

Each day, the student investigator will assess the hardcopies of the data collection forms for missing data. In the case that data that can be collected over the telephone is missing (e.g., socioeconomic information, age, home perception questionnaire measures, etc.), if the missing data is flagged within 60 days of the date of initial collection, study personnel will reach out to the participant and their caregiver via telephone call to collect the measure of interest. If the missing data is flagged outside of the 60-day window of re-collection, the participant will be automatically opted out of that particular measure. In the case that data that must be collected in person is missing (e.g., body composition measures, dimensions of the home environment, hemoglobin concentration, etc.), if the missing data is flagged within 21 days of the date of initial collection, study personnel will reach out to the participant and their caregiver to schedule another home visit to collect the measure of interest (e.g., if measures are missing from the initial home visit, they may be collected in person during the final visit). In the case that the participant or their caregiver has opted out of a particular measure (e.g., hemoglobin concentration), they will not be included in analyses that involve that measure of interest.

**Objective #1:** Describe physical activity levels of the sample of preschoolers in urban Dhaka.

To address our first objective, we will first create a histogram of the distribution of the data to assess the spread and shape of the frequency distribution of each of the categories of all of the physical activity data (average cp15s across all days for each participant). The number of bins within the histogram will be determined using the equation  $1 + 3.3\log_{10}(n)$ . A boxplot will then be created to assess the spread, as measured by the median; interquartile range (IQR); range of observations; presence of outliers; and provide additional information about the shape of the data. Finally, a Q-Q plot will be created to compare the frequency distribution of the data to a normal distribution. Using the shape and direction of the curvature, we will assess any deviation from normality.

We will estimate the mean and 95% confidence interval of cp15s for total physical activity of the sample of children, overall and stratified into the following groups:

- Boys and girls
- BMI categories (underweight, normal, overweight and obese)
- Household food security status (food secure, moderately food insecure; severely food insecure)
- Anemic and non-anemic

We will then summarize the distributions of the average amount (# of minutes) and proportions of wear time spent engaging in SED, LPA, and MVPA, over the measurement period.

Distributions of each time spent in each level of activity will be shown graphically (histograms, kernel density plots) and summarized using conventional descriptive statistics: mean and standard deviation if normally distributed, or median and interquartile range if not normally distributed.

We will then estimate the frequency of children who met Canadian physical activity recommendations on any day, and the average number of days on which children met the recommendations (180 minutes of activity classified as LPA or MVPA, working towards 60 minutes of activity classified as MVPA). Bangladeshi recommended guidelines for preschool-aged children will be used if they are released before statistical analyses begin. These data will be compared to published results in similar international, preschooler populations.

The above analyses will be repeated using data restricted to indoor wear time, in and around the household wear time, on weekdays, and on weekends.

In addition, we will be using the GPS logging data to create ‘heat maps’ for each of the participants’ physical activity locations. This will first be done at the individual level using kernel density estimation and smoothing. These individual ‘heat maps’ can be combined in a master map that will create a visual piece that can aid in describing study findings. We will then use the heat maps for each individual to estimate the average diameter of the ‘sphere’ of activity (km) for the entire study population.

***Objective #2:*** *Estimate the associations between characteristics of the physical environment of the home environment (total area of available floor space inside of the home; frequency that child plays outdoors; number of physical hazards present within the home; number of stationary gross-motor activity-facilitating items present; and number of portable gross-motor activity-facilitating items present) and preschooler activity level.*

To address our second objective, we will first graph each of the variables of interest to assess the data for outliers or implausible data. We will generate histograms, box-plots, and Q-Q plots to assess the following continuous variable:

- Total area of available floor space inside of the home (m^2); Height of stove inside the home (m);

We will generate medians and IQRs for the following discrete, continuous variables:

- Open stairwells in the home (no railing);
- Presence of fine-motor activity-facilitating items;
- Presence of gross-motor activity-facilitating items (for each category).

These discrete, continuous variables may be categorized and treated as categorical variables depending on the data. To assess the linearity between these continuous exposures and outcome measure (using each parameter defined in Section 10.1.), we will create scatterplots and generate the correlation coefficient (Pearson correlation) for each relationship. A locally weighted scatterplot smoother (LOWESS) technique will also be used to check for departures from linearity. If the association between the exposure and the outcome is linear, we will proceed with the linear regression. However, if the association is non-linear, we will proceed with a linear spline model.

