We will then estimate the frequency of children who met Canadian physical activity 24 Hour Movement Guidelines recommendations on any day, and the average number of days on which children met the recommendations for sleep duration (10-13 hours/day). Bangladeshi recommended guidelines for preschool-aged children will be used if they are available at the

time of statistical analyses. These data will be compared to published results in similar international, preschooler populations.

This will be done using the same data files collected from the participant; however, we will only use data from non-waking hours. We will use the ActiLife software to analyze all nighttime activity data and derive variables pertaining to sleep quantity and quality.

We will also compare objectively measured sleep periods (based on accelerometry) with parent reported bedtimes and waking times. This will be done using Individual Manual Inspection (IMI) by comparing bedtimes and waking times reported in the Accelerometry & GPS Log to the computed activity and sleep graphs created in the ActiLife software.

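### Objective 1 reports guideline attainment as children meeting it on any day and an average number of days, without the valid-day denominator that Section 10.1 derives

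*Combined protocol and SAP*

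**What the plan says.** Section 10.1 fixes which days count. On the minimum: "we will use 3 days of data as the minimum number of valid days per child". On the upper end: "If a child has more than 7 days of eligible wear time, we will include all additional days with sufficient wear time". A day is valid with at least 600 minutes of waking wear. Section 9.3.5 sets a target of 7 days, which may be spread over a 14-day window if travel or illness interrupts wear. Section 9.4 allows 7 to 14 days of wear.

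Section 10.1 also derives, for each child, the "proportion of days on which each child reached or exceeded 180 minutes of activity classified as LPA or MVPA". A parallel measure covers the threshold of 60 minutes of MVPA. Both have the child's own days as denominator.

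Section 10.4.1, Objective #1, words the reported summary differently: the "frequency of children who met Canadian physical activity recommendations on any day, and the average number of days" with the guideline met. It states no denominator and no fixed number of days. It then says that these results will be set against published preschooler populations, and that the analyses will be repeated for indoor time, time in and around the household, weekdays and weekends. Section 10.1 defines weekdays as Sunday through Thursday and the weekend as Friday and/or Saturday.

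Objective #4 uses the same form for sleep, including "the average number of days on which children met the recommendations for sleep duration".

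**The concern.** A count of days met depends on how many days were observed as well as on how active the child was. The same is true of having met the guideline at least once. Two groups with identical daily behaviour will differ on both statistics if one has more valid days.

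Two comparisons that the plan states are exposed. Published studies will have their own numbers of valid days, so an external comparison partly reflects protocol and compliance. A full week contains five of the plan's weekdays and two weekend days, so those repeats have unequal denominators even if every child wears the belt perfectly. The quantity that avoids the problem is already derived for activity, but the reporting text does not use it.

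**Working it through.** **The plan's own figure.** The documents give no figure for guideline attainment. Their only calculated figure is the margin of error in Section 9.6: 1.96 × 9.7 / √60 = 2.454, which agrees with the stated 2.45 cp15s. It concerns mean cp15s and is not affected here.

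**Inputs from the documents.** Minimum of 3 valid days and no cap at 7 (Section 10.1); target 7 days (Section 9.3.5); up to 14 days of wear (Section 9.4); weekday and weekend definitions (Section 10.1).

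**Assumed inputs.** The daily probability p of meeting the guideline and the correlation between a child's days. The documents give neither, so ranges are shown.

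**Formulas, for k valid days.**
- Ever met, independent days: 1 − (1 − p)^k
- Expected days met: k × p
- Expected proportion of days met: (k × p) / k = p

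**Worked case.** At p = 0.2, ever met is 1 − 0.8³ = 0.488 with 3 days and 1 − 0.8⁷ = 0.790 with 7.

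| p | Ever met, k = 3 / 7 / 14 | Expected days met, k = 3 / 7 / 14 | Proportion of days, any k |
|---|---|---|---|
| 0.1 | 27% / 52% / 77% | 0.3 / 0.7 / 1.4 | 0.1 |
| 0.2 | 49% / 79% / 96% | 0.6 / 1.4 / 2.8 | 0.2 |
| 0.3 | 66% / 92% / 99% | 0.9 / 2.1 / 4.2 | 0.3 |
| 0.5 | 88% / 99% / >99.9% | 1.5 / 3.5 / 7.0 | 0.5 |
| 0.9 | 99.9% / >99.9% / >99.9% | 2.7 / 6.3 / 12.6 | 0.9 |

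The 3-versus-7 contrast is the one to weigh. Fourteen days is the outer limit.

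**Correlated days.** A beta-binomial with within-child correlation 0.4 gives, for 3 / 7 / 14 days, 19% / 27% / 34% at p = 0.1, 50% / 64% / 73% at p = 0.3, and 97% / 99% / 99.6% at p = 0.9. The rise is less steep but remains. The expected count is still k × p.

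**Weekdays against weekends, perfect 7-day wear, same p on every day.**
- p = 0.3, ever met: 1 − 0.7⁵ = 0.832 on weekdays; 1 − 0.7² = 0.510 on weekends.
- p = 0.3, days met: 5 × 0.3 = 1.5; 2 × 0.3 = 0.6.
- p = 0.3 with within-child correlation 1/3 (beta-binomial 0.6, 1.4), ever met: 62% and 44%.
- p = 0.9, ever met: above 99.9% and 99%; days met: 4.5 and 1.8.

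The proportion of days has expectation p in every row, provided that the number of valid days is unrelated to activity.

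**The case against.** The strongest reply is that the plan already commits to the right measure. Section 10.1 specifies the proportion of days for both thresholds, and also mean minutes per day in each category. This stands: a reader might infer that the plan has no attainment measure free of the number of days, and that would be wrong. What is missing is the link from that derivation to the figures that Section 10.4.1 reports and compares.

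'On any day' could also mean on any given day, which would not depend on valid days. That reading is open, so the first statistic is ambiguous rather than certainly at fault. It does not help the second statistic, which is a count.

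The any-day effect may be small. On a valid day of at least 600 minutes, 180 minutes is at most 180/600 = 30% of wear, and everything above 48 cp15s counts, so p could be high. This is fair, and the table shows almost no movement at p = 0.9. The count still scales with days there. Restricting the analysis to indoor or near-home minutes on the same days cannot raise p.

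A reader might also infer that attainment will be compared by sex, BMI, food security and anemia. The documents do not say so: in Objective #1 those groups attach to mean cp15s, and in Objective #4 they attach to distributions of sleep measures. Nor is attainment the main result. The primary measure is mean cp15s, which alone drives the sample size. Finally, 14 valid days should not be read as typical: 7 is the target, the final visit is arranged once 7 days are complete, and days of travel or illness are excluded.

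**Conclusion.** The point holds as a mismatch between Sections 10.1 and 10.4.1, and it should be corrected before analysis. The count of days met is proportional to valid days whatever the daily probability. The any-day figure rises with valid days if it means 'ever' and p lies strictly between 0 and 1. From 3 to 7 valid days the any-day rise is 30 points at p = 0.2 and 26 points at p = 0.3 with independent days, 14 points at p = 0.3 with correlation 0.4, and negligible at p = 0.9. The true size is unknown because the documents give neither p nor the correlation.

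The clearest consequence is internal. With identical behaviour on every day, full wear and p = 0.3, the weekday and weekend repeats would show 83% against 51%, and 1.5 against 0.6 days. The external comparison is exposed in the same way when other studies have different numbers of valid days.

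For sleep the same form is used, but a reader should not assume that the remedy is already in place. Section 10.1 derives no proportion of nights within 10 to 13 hours and gives no rule for an eligible night. The 3-day and 600-minute rules concern waking wear. Mean cp15s and the sample size are unaffected.

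**What to change.** **Objective #1 (Section 10.4.1).**
- Make the per-child proportion of valid days from Section 10.1, for each threshold, the reported attainment summary: its mean across children with a child-level 95% CI.
- Use it for the weekday, weekend, location-restricted and external comparisons.
- State whether 'on any day' means ever or on any given day.
- If a count or an ever-met figure is kept, report the distribution of valid days beside it.

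**Objective #4.**
- Define an eligible night in Section 10.1.
- Derive each child's proportion of eligible nights with 10 to 13 hours of sleep, and report it in the same way.

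**Cost.** Wording in Sections 10.1 and 10.4.1, plus one simple derived sleep variable. No new data and no change to the sample size. The attainment figure may look less favourable than an ever-met percentage.
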